Background: Oral lichen planus (OLP) is a chronic inflammatory mucocutaneous disease with uncertain etiology. It may appear as bilateral white striations, papules, plaques, erythema, erosions and blisters on the buccal mucosa, tongue and gingiva.

Conventionally, corticosteroid treatments are used as a treatment in Erosive OLP. As an alternative method to steroid therapies Diode lasers were introduced for the symptomatic relief of pain and burning sensation with no adverse effects.

Study objective: the objective of the study is to compare the effect of topical corticosteroid and 980nm Diode Laser in the treatment of erosive OLP.

Materials and Methods: This study will be conducted on 44 patients histologically diagnosed erosive OLP. Patients will be divided into two groups: Group I: 22 patients will be given conventional treatment (topical corticosteroid), Group II: 22 patients will be treated with 980nm Diode Laser. The pain score, clinical and biochemical evaluation will be done at the beginning of the treatment, 6 weeks and 12 weeks after treatment. The evaluation will be done using Visual Analogue Scale (VAS) for pain assessment, the criteria scale described and modified by Thongprasom et al 2003 for clinical assessment, and oxidative stress biomarker analysis for the biochemical evaluation.

Results: The data obtained will be collected and statistically analyzed.

Keywords: Oral lichen planus, 980 nm Diode Laser, topical steroid therapy.

Introduction

Oral lichen planus (OLP) is a chronic inflammatory mucocutaneous disease, which affects the skin, nails, hair and mucous membranes, recognized in 1866. ¹ It affects 1%–2% of the population at middle age, with a female predominance. OLP etiology is unknown but evidence suggests that this disease is an immune-mediated process involving cytotoxic T cells as well as the release of a diverse array of proinflammatory cytokines that lead to the apoptosis of epithelial cells. ²

Although the immunological system plays a substantial role in OLP, other factors may be also involved, such as psychological stress, drug intake, anxiety and some systemic diseases, including hepatitis C virus infection, hypertension, diabetes, and graft-vs-host disease. However, the precise role of most of these conditions in OLP remains unclear.³

Oxidative Stress (OS) may play a central role in the etiology of OLP as the sub epithelial infiltration of T lymphocytes in OLP contributes `to the local production of cytokines, which can stimulate production of ROS.⁶

OS affects the normal intracellular balance, producing excessive oxidant substances, i.e., reactive oxygen species (ROS) and reactive nitrogen species (RNS) resulting in a relative deficiency of enzymatic and non-enzymatic antioxidants as well as oxidation of unsaturated fatty acids in cell membranes or lipoproteins inducing lipid peroxidation.⁷

Research has demonstrated that increased lipid peroxidation in cell membrane can stimulate inflammatory and immune responses. Malondialdehyde (MDA) as the most important product of lipid peroxidation can be used as a marker for the measurement of oxidative stress. Higher levels of MDA were reported in saliva of patients affected by OLP.⁸

3

Oxidative stress can be evaluated by the measurement of total antioxidant capacity (TAC) in biological fluids. Since the body antioxidants are highly varied, use of an index that measures total capacity of antioxidants in biological fluids, such as TAC, could be a new and suitable method.⁸

As a diagnostic fluid which may be easily collected, saliva is used for the measurement of markers of oxidative stress (OS) associated with local oral conditions.⁶

Clinically, OLP may affect several sites of the oral cavity and several clinical manifestations are reported, according to Andreasen classification system: reticular (Wickham's striae), papular, plaque-like "white form", atrophic (erythematous), erosive-ulcerous and bullous-erosive "red form"; however, the classic lesions are bilateral, symmetric and composed mainly of a reticular pattern.⁴

It is a challenge to diagnose OLP, particularly in the absence of the classic reticular pattern on oral mucosal surfaces. Therefore, an oral biopsy with histopathological examination is usually required to confirm the clinical diagnosis and exclude dysplasia and cancer. ^{3, 4, 5}

Symptoms associated with OLP are variable, ranging from no symptoms to severe pain. About two-thirds of the patients describe a burning sensation and pain in the area of the oral mucosa, which leads to difficulties and restrictions in eating, speaking and swallowing.⁹

The asymptomatic forms usually do not need management with drugs; they are periodically followed up by clinicians, while the clinical management and treatment in symptomatic patients is often required. However, the treatment of OLP is not curative, in fact its efficacy is related to the symptoms control and ulcers management (especially in erosive OLP). ^{9,10}

4

The conventional treatment of Symptomatic OLP is usually high potency topical corticosteroids, systemic prednisone or immunosuppressive agents like cyclosporine, tacrolimus and thalidomide.^{10,11} However, long-term treatment with topical corticosteroids may cause obvious side effects, such as local pigmentation, oral candidiasis and dry mouth. Additionally, some studies reported persistent lesions with treatment resistance increasing the risk of cancer transformation.¹¹

In this context, alternative therapies capable of relieving OLP symptoms with minimal or no side effects. Lasers emerge as an option for OLP treatment due to its known ability to reduce pain, resolve inflammation and promote tissue repair in different pathological conditions.¹²

Different types of lasers with different wavelengths have been utilized in the treatment of OLP. ND:YAG, CO2 laser and Low-intensity lasers (LLLT) had a remarkable effect on pain, size of lesions and also clinical response.¹²

Several LLLT have been used to treat oral lichen planus, but more recently, diode (a spectrum of red to infrared wave lengths, 600 to 1100 nm) lasers. These lasers have been used with different wave lengths, intensities, powers, durations, number of sessions, and therapeutic approaches. ^{13,14}

Patients with OLP who were treated by low level laser therapy (LLLT) with wavelength of 980 nm reported acceptable results in short follow-up studies, this may be due to the effect of LLLT on soft tissues.¹⁵

Physiologic effects of LLLT on tissues are primary and secondary. Primary effects consist of enhancement of blood flow, lymph drainage, cellular metabolism, neutrophil and fibroblast activation, and pain stimulation threshold. Secondary effects include aggregation of prostaglandins, immunoglobulins and

lymphokines, as well as beta-endorphin and encephalin in the tissue, decreasing the inflammation, immune response, and pain, respectively. ¹⁵

However, the efficacy of laser in OLP treatment remains uncertain. Some studies have shown that conventional therapy with topical corticoids showed better control of OLP pain and size when compared to lasers. ¹⁴ On the other hand, other studies have demonstrated comparable outcomes for patients treated with both laser and corticoids. However, these studies used different laser parameters and no protocol for laser could be established. ^{15,16}

These different results of laser therapy may need further investigations to resolve the conflict and to assess the effectiveness of LLLT in treatment of OLP.

The purpose of this study is to evaluate the effectiveness of 980nm Diode Laser in the treatment of erosive OLP in relation to conventional corticosteroids.

The null hypothesis of this research is that there will be no statistically significant difference among the test group treated by 980nm Diode Laser and the control group treated by conventional therapy.

AIM OF THE STUDY

The aim of the study is to evaluate the effect of 980nm Diode Laser in the treatment of erosive OLP compared with conventional topical corticosteroid therapy.

Primary Objective

To evaluate clinically on Visual Analogue Scale (VAS) the ability of 980nm Diode Laser to control pain compared with topical corticosteroid.

Secondary Objective

To test the clinical improvement of OLP according to Thongprasom et al 2003 scoring system and to evaluate the oxidative stress in saliva biochemically.

FLOW CHART STUDY DESIGN

PLAN OF THE STUDY

Material and Methods

I. Material

i. Study design and setting:

This randomized, controlled, clinical trial will be conducted on 44 patients of both sexes who complain from erosive OLP. They will be selected from the outpatient clinic of Department of oral medicine, Faculty of dentistry.

Patients will be given a detailed explanation of the study and will sign an informed consent form according to the guidelines of the Ethical Committee of the Faculty of Dentistry, Alexandria University. They will be treated according to the principles of the modified Helsinki's code for human clinical studies (2013).¹⁷

Inclusion Criteria

- Patient histologically diagnosed with erosive OLP based on WHO modified criteria 2003. ¹⁸
- 2. Patients 30-70 years of age.
- 3. Presence of painful erosive OLP lesions diagnosed by biopsy.¹⁸

Exclusion Criteria

- 1. Pregnant or breast-feeding women.¹⁸
- 2. Patients currently treated for cancer with Chemotherapy or Radiotherapy.¹⁵
- 3. Patient currently on Corticosteroid therapy or had been on treatment on the past 3 months.¹⁸

- 4. Those who had used Anti-inflammatory drugs topical or systemic in the last month.²
- 5. Those who reported use of drugs related to Oral Lichenoid Lesions.²
- 6. Presence of Amalgam restorations near the OLP lesions.²⁰
- 7. Those with description of dysplasia in histopathological examination. ²⁰
- 8. Patients suffering from any uncontrolled systemic diseases (such as diabetes, cardiovascular, liver disorder, renal dysfunction)²⁰
- 9. Patients with findings of any physical or mental abnormality which would interfere with or be affected by the study procedure. ²
- 10.Patients with skin lesion.

ii. Sample size calculation:

Sample size will be estimated assuming confidence level = 95% and study power = 80%. The mean (SD) reported pain scores measured by the Visual Analogue Scale after 3 months for the laser group was 0.79 (1.23) and for the steroid group was 2.81 (2.84). The minimum sample size was calculated to be 20 patients, increased to 22 patients per group to make up for possible loss to follow up.

The total sample size = number of groups \times number per group= 2 X 22= 44 patients.

Sample size was based on Rosner's method calculated by G power 3.0.10. 21, 22, 26

II. Methods

Randomized Controlled Clinical Study

The purpose and nature of the study will be explained for the selected 44 patients and an informed consent will be obtained from patients who agree to participate in this study prior to any procedure.

An incisional biopsy will be performed under local anesthesia from the lesion to exclude dysplasia and cancer.

Grouping and Randomization

The selected patients will be randomly assigned to the following groups:

Group I (Control group)

22 patients will be given topical corticosteroid 0.1% topical triamcinolone acetonide preparation (0.1% triamcinolone acetonide orabase, Kenacort-A Orabase Pomad, DEVA HOLDING A.Ş, Istanbul, Turkey) three times daily for 4 weeks.

The application should be in one direction with no food or fluid after administration for a minimum of 1 hour post application. Also, patient will be applying miconazol oral gel once daily to avoid superimposed fungal infection.²⁰

Group II (Study group)

22 patients will be subjected to laser therapy by the 980 nm diode laser (MEDENCY ,PRIMO – Vicenza Italy) for photobiomodulation (PBM) and the treatment will be continued up to 10 sessions (2 sessions per week).

A Fiber Tip with a diameter of $400\mu m$ will be used. The output power will be 300 mW and the average power density about 1 W/cm². A "spot" technique will be used, with a slight overlapping in order to evenly distribute energy covering all the mucosal lesions and also the peri-lesional tissues up to 0.5 cm.

Each session will be performed delivering a fluence of 4 J/cm2 per lesion, and the probe will be held perpendicularly at a distance of about 2 mm. The time of delivery per point of application is approximately 4 Sec in continuous wave with 2 sessions weekly. After each laser session, a cold diet will be recommended. ^{20,22}

Allocation concealment

Allocation of cases will be via block randomization method using a computer generated random sequence into 2 groups of equal numbers (N=22 patient/ group).²⁷

Allocation will be informed by a trial independent individual. The participant allocation will be kept in opaque, sealed envelopes and arranged sequentially by a dental assistant, who will not be involved in the study.

Each envelop will be opened after completing the oral examination and right before the application of the intervention.

A) After biopsy and before treatment:

1. Detailed medical and dental history will be obtained from the selected patients.

2. Thorough intraoral examination will be performed to determine the need for scaling and treatment of any source of irritation.

3. Oral hygiene instructions will be carried out to all patients.

4. Adequate hydration will be advised.

5. Every group of patients will be given their treatment protocol.

B) During and after treatment:

Clinical Evaluation:

All patients will be clinically and biochemically evaluated before treatment, after 6 and 12 weeks with following criteria:

1- Subjective assessment

Discomfort and pain severity will be reported by each patient using Visual Analogue Scale (VAS). The VAS consisted of a 10-cm horizontal line marked 0 (=

no pain) to 10 (= most severe pain ever experienced). Patients will be requested to mark the scale at each visit, before and after treatment for each group. Complete resolution of the symptoms (no symptoms) will be defined as the absence of any discomfort, corresponding to a zero VAS score.

The stability of the results in the follow-up period will be also described. ^{20, 22}

2- Objective assessment

- The size of the lesion and the healing pattern will be monitored. The clinical data will be scored according Thongprasom et al 2003 scoring system. Score 5: white striae with erosive area >1 cm2, Score 4: white striae with erosive area <1 cm2, Score 3: white striae with erythematous area >1 cm2, Score 2: white striae with erythematous area <1 cm2, Score 1: mild white striae only, Score 0: no lesions, normal mucosa. ^{2,24}
- Measurement of Total Oxidative Stress in saliva including Total antioxidant capacity (TAC) and malondialdehyde (MDA). Saliva will be collected before treatment and after 6 and 12 weeks. Saliva will be collected, centrifuged at 30 g for 10 min to evacuate cellular debris and microscopic organisms. The filtered saliva will be stored at -80°C until the time of the biochemical investigation (Tvarijonaviciute, Aznar-Cayuela, Rubio, Ceron, & López-Jornet, 2017). The determination will be measured using the established colorimetric method (Koracevic, Koracevic, Djordjevic, Andrejevic, & Cosic, 2001). Biochemical analysis will be conducted at the Department of Biochemistry, Faculty of Medicine, Alexandria University.²⁵

3- Photographs:

Photographs will be taken at baseline and at the end of the study.

STATISTICAL ANALYSIS

The data will be processed and analysed using Statistical Package for Social Sciences program SPSS software^{*}.

^{*} Armonk, NY: IBM Corp, USA.

ETHICAL CONSIDERATIONS

The clinical part of the study will be performed after the approval of the Research Ethics Committee, Faculty of Dentistry, Alexandria University.

The volunteers will provide written informed consent and the study will be conducted in accordance with the modified Helsinki Declaration of 2013.¹⁴

The patients will receive written consent about the study protocol before agreeing to participate in the study. The patients will have the right to withdraw at any time during the study.

Clinical trials need written informed consent in order to clarify objectives, risks and benefits of the study.

Medical therapy for potential risks will be provided (cortico steroids will be administered in case of severe pain after laser treatment).

DURATION OF THE STUDY

| Months Study activities | 1 | 2 | 3 | 4 | 5 | 6 | 7 | 8 | 9 | 10 | 11 | 12 |
|--|---|---|---|---|---|---|---|---|---|----|--------------|--------------|
| Purchase of materials | ~ | > | | | | | | | | | | |
| Patient selection and Clinical study | | | ~ | ~ | ~ | ~ | ~ | ~ | | | | |

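### Does the unnamed starting point of the 6- and 12-week visits undermine the pain comparison?

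*Protocol*

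**What the plan says.** Three places in the protocol set the visit schedule.

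- **Abstract, Materials and Methods:** "The pain score, clinical and biochemical evaluation will be done at the beginning of the treatment, 6 weeks and 12 weeks after treatment".
- **B) During and after treatment, Clinical Evaluation** (covers the VAS): "All patients will be clinically and biochemically evaluated before treatment, after 6 and 12 weeks with following criteria".
- **2- Objective assessment**, for the biochemistry: "Saliva will be collected before treatment and after 6 and 12 weeks".

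The two treatments differ in length. Steroid is applied "three times daily for 4 weeks". For laser, "the treatment will be continued up to 10 sessions (2 sessions per week"; no minimum number of sessions is given.

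The Primary Objective names the VAS but no visit: "To evaluate clinically on Visual Analogue Scale (VAS) the ability of 980nm Diode Laser to control pain compared with topical corticosteroid". The sample size section relies on "reported pain scores measured by the Visual Analogue Scale after 3 months", and does not say from what point those 3 months ran. Week 0 is not defined anywhere in the protocol.

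**The concern.** The abstract mentions the beginning of treatment and then counts weeks after treatment, which can be read as counting from the last dose or session. The two methods sentences name a pre-treatment assessment and then 6 and 12 weeks, which reads most naturally as counting from baseline. On the first reading, visit dates depend on how long treatment lasted. They would therefore differ by arm and, within the laser arm, by the number of sessions received.

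The outcome concerned is VAS pain, which is primary. The Introduction says that treatment controls symptoms and does not cure, so the score may well depend on how long ago treatment stopped. If some patients were seen on one calendar and some on the other, no later analysis could put them back on a common one. An analysis plan can select a visit but cannot move one already held.

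**Working it through.** **1. The plan's own figure.** The inputs, from the sample size section, are 3-month VAS means (SD) of 0.79 (1.23) for laser and 2.81 (2.84) for steroid, 95% confidence (taken as two-sided 5%) and 80% power.

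- Difference: 2.81 − 0.79 = 2.02.
- SD: √((1.23² + 2.84²)/2) = 2.188.
- Standardised difference: 2.02/2.188 = 0.923.
- The two-sample t-test has power 0.791 with 19 per group and 0.812 with 20. The stated 20 per group is reproduced (the normal approximation gives 19).

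The visit origin does not enter this calculation, so neither reading changes the sample size.

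**2. When treatment ends.** Steroid: week 4. Laser with n sessions at 2 per week: (n − 1) × 3.5 days if sessions are evenly spaced from day 0 (an assumption), or n/2 weeks if whole weeks are counted. For n = 10 this is 31.5 days = 4.5 weeks, or 5 weeks.

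**3. Visit dates, in weeks from the start of treatment.**

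| Origin | Steroid | Laser, 10 sessions | Laser minus steroid |
|---|---|---|---|
| Start | 6 and 12 | 6 and 12 | 0 |
| End | 4 + 6 = 10 and 4 + 12 = 16 | 10.5–11 and 16.5–17 | +0.5 to +1 |

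**4. Weeks since treatment ended, at the same visits.**

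| Origin | Steroid | Laser, 10 sessions | Laser minus steroid |
|---|---|---|---|
| Start | 6 − 4 = 2 and 12 − 4 = 8 | 1–1.5 and 7–7.5 | −1 to −0.5 |
| End | 6 and 12 | 6 and 12 | 0 |

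**5. Shorter laser courses.** The protocol gives no minimum, so these are assumptions. Counted from the end, the 12-week visit falls at week 15.5–16 after 8 sessions and week 14.5–15 after 6. Against steroid at week 16, the gap is −0.5 to 0 weeks and −1.5 to −1 weeks. With 10 sessions it is +0.5 to +1, so the sign of the gap depends on the number of sessions.

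**6. The sentences side by side.** The abstract's phrase can loosely mean after treatment began. On that reading it agrees with both methods sentences on weeks 6 and 12 from baseline. No sentence states an end-of-treatment origin outright, and none rules out a baseline origin. The promise, under the VAS assessment, to describe stability during follow-up does not say when follow-up begins and does not settle the matter.

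**The case for a change.** The best case for a change is that the protocol, and not an analysis plan, fixes when patients are seen. Two reasonable readings put the same visit 4 weeks apart for steroid and 4.5 to 5 weeks apart for a full laser course. The 6-week visit is affected too: it falls about 1 to 2 weeks after treatment on one reading and 6 weeks after on the other. A badly timed visit cannot be recovered, and naming the origin costs a few words and no extra visits.

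The arithmetic stands, and so does the observation that week 0 is undefined. The step from there to harm does not. It needs patients in one trial to be scheduled on different origins. The protocol describes a single outpatient clinic and a twelve-month thesis project, and nothing suggests that visits would be booked from the abstract instead of the methods section. With one origin used throughout, the 4- to 5-week figure has no effect on the contrast between arms.

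The case for prescribing a start-of-treatment origin is weaker still. That choice equalises calendar time and leaves the arms 0.5 to 1 week apart in time off treatment. An end-of-treatment origin does the reverse. Nor can a start-based week 12 be said to match the 3-month score behind the sample size, because the protocol does not say how those months were counted. Which visit is primary is a separate question, which an analysis plan not shown here may settle.

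**Conclusion.** The wording is loose, but the schedule is not contradictory and the comparison is not put at risk. Visits at weeks 6 and 12 from baseline satisfy all the scheduling sentences. If the clinic instead counted from the end of treatment in both arms, the arms would be seen 0.5 to 1 week apart for a full laser course. Under the assumed 6-session course the laser visit would come up to 1.5 weeks earlier than the steroid visit. Nothing in the document shows that pain scores change materially over such intervals, and no direction of bias can be derived. The 20 per group is reproduced and does not depend on the answer.

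This conclusion assumes that one origin is used for all patients and for the VAS, clinical score and saliva alike, which is the ordinary way to run such a schedule. Writing that origin down would be tidy, but it would only record a detail that the study team can be expected to fill sensibly. No change to the plan follows.

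### Laser is justified partly by tolerability, yet no recording of side effects is planned in either arm, nor of corticosteroid given to laser patients

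*Protocol*

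**What the plan says.** **Rationale.** The protocol's opening summary states that "Diode lasers were introduced for the symptomatic relief of pain and burning sensation with no adverse effects". The Introduction warns that "long-term treatment with topical corticosteroids may cause obvious side effects, such as local pigmentation, oral candidiasis and dry mouth", and then turns to "alternative therapies capable of relieving OLP symptoms with minimal or no side effects", with lasers as the option. It adds a second reason for the trial: "However, the efficacy of laser in OLP treatment remains uncertain", because earlier studies conflict.

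**Objectives.** The primary objective is "To evaluate clinically on Visual Analogue Scale (VAS) the ability of 980nm Diode Laser to control pain compared with topical corticosteroid". The secondary objective covers the Thongprasom score and salivary oxidative stress. Neither mentions side effects.

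**Evaluations.** Clinical Evaluation states: "All patients will be clinically and biochemically evaluated before treatment, after 6 and 12 weeks with following criteria". The items that follow are the VAS, lesion size and healing with the Thongprasom score, salivary TAC and MDA, and photographs at baseline and study end.

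**Harm.** Two places foresee it. Group I applies a daily miconazole gel to prevent fungal infection. Ethical Considerations says that "cortico steroids will be administered in case of severe pain after laser treatment". Neither is linked to data collection.

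**The concern.** Two things are at stake.

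1. **Tolerability.** The Introduction reports that some studies found steroid better and others found the two treatments comparable. If this trial finds similar pain control, tolerability will weigh heavily in choosing between them, and the trial would have no planned data on it.
2. **Reading the primary outcome.** Corticosteroid given to a laser patient is both a sign of harm and exposure to the comparator drug class. It could lower that patient's VAS. The Exclusion Criteria bar anyone with corticosteroid treatment in the past 3 months, so the protocol itself regards such exposure as relevant. During the trial, nothing visible requires it to be noted.

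This is not a matter for a statistical analysis plan. Which observations are made at visits is fixed in the protocol, and a later analysis cannot recover events that nobody recorded.

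**Working it through.** **1. What the protocol raises, against what it plans to record**

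| Effect or event | Where it is raised | Planned record |
|---|---|---|
| Pigmentation, dry mouth | Introduction | None |
| Candidiasis | Introduction; Group I (miconazole) | None |
| Severe pain after laser | Ethical Considerations | VAS only; session coverage unclear |
| Corticosteroid for that pain | Ethical Considerations | None |

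A new erosion or burn at the treated site might show in the lesion score, but not as an event with a date or cause. The VAS is to be marked at each visit, before and after treatment. That could mean every laser session or only the evaluations at 0, 6 and 12 weeks.

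**2. Timing of the existing visits**

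The steroid course lasts 4 weeks. Laser runs to at most 10 sessions at 2 per week, so 10 / 2 = 5 weeks. If weeks are counted from the start of treatment, the 6-week visit falls 6 − 4 = 2 weeks after steroid ends and 6 − 5 = 1 week after the last laser session. The opening summary can be read as counting from the end of treatment, in which case the gap is 6 weeks in both arms. Either way, a check of current status alone would miss events during treatment, so the question must cover the time since the previous visit.

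**3. The numbers per arm**

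The protocol's 20 per group can be reproduced from its own VAS figures. The difference is 2.81 − 0.79 = 2.02. The SD is √((1.23² + 2.84²)/2) = 2.188, so d = 2.02 / 2.188 = 0.923. A two-sided t-test at 5% (sidedness assumed) with 80% power needs 19.43, hence 20, raised to 22 for loss to follow-up. This calculation concerns pain only. It supplies the denominators below.

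**4. What recording would yield**

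Upper limit when no events are seen in n patients: 1 − 0.05^(1/n) one-sided 95%, and 1 − 0.025^(1/n) for the exact two-sided 95% interval.

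| n | One-sided | Two-sided |
|---|---|---|
| 22 | 12.7% | 15.4% |
| 20 | 13.9% | 16.8% |

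The chance of at least one event among 22 is 1 − (1 − p)^22. For assumed true rates of 5%, 10% and 20% (the protocol gives none) it is 68%, 90% and 99%.

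For a comparison between arms of 22, two-sided Fisher p for 0 versus 4 events is 2 × C(22,4)/C(44,4) = 2 × 7315/135751 = 0.11. For 0 versus 5 it is 2 × 26334/1086008 = 0.049. A formal test would therefore detect only large differences.

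**5. Effect of unrecorded corticosteroid on the laser arm's VAS**

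Each point of relief in one patient moves the mean of 22 by 1/22 = 0.045. Shifting the mean by a tenth of the planned difference, 0.202, takes 0.202 × 22 = 4.4 patient-points in total. The protocol gives neither how often this treatment is expected nor its effect, so the actual shift cannot be estimated. Without a log it could not be estimated afterwards either.

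**The case against.** Much can be said for the protocol as it stands.

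- **The trial is about efficacy.** A reader might infer that it cannot test its own rationale. The text does not support that: the Introduction gives uncertain and conflicting efficacy as the reason for the study, and the aim and objectives concern effect on pain, lesions and oxidative stress. All of these can be addressed. Only the tolerability part of the rationale is left untested.
- **Some harm may show.** A reader might infer that there will be no safety data at all, or that pain after laser is wholly unrecorded. That goes too far. VAS marks before and after treatment, monitoring of lesion size and healing, and photographs could reveal local worsening. They do not capture candidiasis, dry mouth, pigmentation or corticosteroid use.
- **The named steroid effects belong to long-term use.** The course here is 4 weeks, with antifungal prophylaxis. Recording side effects would not turn this into a test of long-term steroid harm. This stands and limits what may be concluded.
- **The numbers are small.** The zero-event limits are generic to any arm of this size and measure no error in the plan. This also stands: the data would be descriptive.
- **The evaluation list is not declared exhaustive, and some pages and the flow chart are not shown.** The point therefore rests on the visible text. That text fixes objectives, visits and measurements in some detail without any side-effect item.

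**Conclusion.** The point holds in a limited form. Tolerability is one stated reason for laser, and corticosteroid for severe pain after laser is foreseen. The visible objectives and evaluations nevertheless plan no recording of side effects in either arm or of that treatment. As written, the trial can offer nothing planned on comparative tolerability, and the laser arm's VAS would have to be read without knowing who received the comparator drug class.

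The efficacy comparison is not invalidated. Nor can it be said that the VAS result will be biased, since the frequency and effect of the corticosteroid treatment are unknown. The gain from recording is modest: with no events, an upper limit of about 15% with 22 patients or 17% with 20 completers. It is still worth having because it costs little and cannot be recovered later.

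Separately, the opening summary's statement that laser has no adverse effects and the potential risk named in Ethical Considerations need to be reconciled.

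**What to change.** - Add to the list under Clinical Evaluation a short structured side-effect check at 6 and 12 weeks, identical in both arms, asking about events since the previous visit: candidiasis, dry mouth, pigmentation, mucosal burn or new ulcer, and any other event.
- Log, with its date, every use in the laser arm of the corticosteroid foreseen in Ethical Considerations.
- State whether the VAS before and after treatment is marked at each laser session or only at the evaluation visits.
- Report counts and percentages by arm with exact 95% confidence intervals, as description only. Base any comparison on the common 6- and 12-week checks, because laser patients attend more often. Note that candidiasis in the steroid arm is observed under antifungal prophylaxis, and draw no conclusion on long-term steroid harms.
- Reconcile the opening summary's wording on adverse effects with the risk named in Ethical Considerations.

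**Cost:** one form page, a few minutes per existing visit and one descriptive table. No extra patients or evaluation visits are needed, and no treatment rule changes.
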